- Blood samples for RNA sequencing (messenger ribonucleic acid [mRNA] sequencing analysis) will be collected before vaccine administration (Day 0), at Dose 2 (Day 28), one day post-Dose 2 (Day 29), at Dose 3 (Day 196), and one day post-Dose 3 (Day 197) for subjects from **AduFx, 2PedFx, PedFx, and Adu2Fx groups** and before vaccine administration (Day 0), one month post-Dose 1 (Day 28), at Dose 2 (Day 196) and one day post-Dose 2 (Day 197) for subjects from **Adu1Fx group**.
- Blood sample for assessment of parasitemia (PCR testing) will be collected on the day of subject entry into the hotel phase (Day 295 [Visit 16]) to provide an estimate of the number of subjects likely to develop malaria within the first few days of the hotel phase.

- Blood sample for assessment of parasitemia (blood smear) will be collected daily for 14 days (from Day 291 [Visit 12] to Day 304 [Visit 25]) and then every two days for nine days (Day 306 [Visit 26], Day 308 [Visit 27], Day 310 [Visit 28], Day 312 [Visit 29], and Day 314 [Visit 30]). For subjects who develop malaria, blood smear may be discontinued once the subject has three consecutive negative smears (separated by more than 12 hours) following the initial treatment.
- Blood samples for testing of human immunodeficiency virus (HIV), hepatitis C virus (HCV) and HBsAg will be collected from all subjects at screening.
- Urinary pregnancy test (urine beta-human chorionic gonadotropin [β -HCG]) will be performed on all women at screening, before each vaccine dose for vaccinated subjects and on the day of challenge.
- Type of study: self-contained.
- Data collection: electronic Case Report Form (eCRF).
- Safety monitoring:
 - Each subject will be observed for at least 30 minutes after vaccination to evaluate and treat any acute AEs.
 - Each subject will be observed for at least 30 minutes following completion of the sporozoite challenge to evaluate and treat any acute allergic reactions.
 - All SAEs (all, fatal, related to the investigational vaccine) and pregnancies will be reported until study end (Day 376).
 - All AEs and SAEs leading to withdrawal from further vaccination will be reported until study end (Day 376) for all vaccinated subjects (AduFx, 2PedFx, PedFx, Adu2Fx, and Adu1Fx groups).
 - Meningitis and potential immune-mediated diseases (pIMDs) are AEs of specific interest to be reported until study end (Day 376) for all vaccinated subjects (AduFx, 2PedFx, PedFx, Adu2Fx, and Adu1Fx groups).

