11.2.3. Safety

- Safety and reactogenicity of the investigational vaccine for each vaccination schedule:
 - Occurrence of solicited local and general AEs within seven days (day of vaccination and six subsequent days) after each vaccination.
 - Occurrence of unsolicited AEs within 30 days (day of vaccination and 29 subsequent days) after each vaccination, according to the Medical Dictionary for Regulatory Activities (MedDRA) classification.

- Occurrence of AEs within 30 days (day of challenge and 29 subsequent days) after challenge, according to the MedDRA classification.
- Occurrence of SAEs (all, fatal, related to investigational vaccine) within 30 days (day of vaccination and 29 subsequent days) after each vaccination, according to the MedDRA classification.
- Occurrence of SAEs (all, fatal, related to investigational vaccine) during the whole study period (from Dose 1 [Day 0] up to study conclusion [Day 376]), according to the MedDRA classification.
- Occurrence of AEs and SAEs leading to withdrawal from further vaccination from Dose 1 (Day 0) up to study conclusion (Day 376), according to the MedDRA classification, for each vaccinated subject.
- Occurrence of pIMDs from Dose 1 (Day 0) up to study conclusion (Day 376), according to the MedDRA classification, for each vaccinated subject.
- Occurrence of meningitis from Dose 1 (Day 0) up to study conclusion (Day 376), according to the MedDRA classification, for each vaccinated subject.
- Occurrence of abnormal laboratory values at screening, Day 35, Day 58, Day 203, Day 226, the day of first parasitemia, and Day 314 for each vaccinated subject and at screening, the day of first parasitemia and Day 314 for the infectivity control subjects.
- Safety after sporozoite challenge in the infectivity control group.
 - Occurrence of AEs within 30 days (day of challenge and 29 subsequent days) after challenge, according to the MedDRA classification.
 - Occurrence of SAEs (all, fatal, related) from day of challenge (Day 286) to the end of the challenge phase (Day 314), according to the MedDRA classification.

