11.11. Interpretation of analyses

For the primary efficacy evaluations the aim will be to establish significant vaccine efficacy over infectivity controls whereas secondary efficacy evaluations between vaccination schedules will be descriptive with the aim to characterize the difference in immunogenicity, efficacy and safety between groups.

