2. STUDY DESIGN

Figure 1 Study design

D: Day; Mth: month; R: RTS,S; SCR: Screening; V: visit. * Blood sample for estimation of subjects with parasitemia (PCR testing) will be collected on the day of subject entry into the hotel phase (Day 295 [Visit 16]); blood sample for biochemistry and hematology parameters will be collected the day of first parasitemia and blood sample for assessment of parasitemia (blood smear) will be collected daily for 14 days (from Day 291 [Visit 12] to Day 304 [Visit 25]) and then every two days for nine days (Day 306 [Visit 26], Day 308 [Visit 27], Day 310 [Visit 28], Day 312 [Visit 29], and Day 314 [Visit 30]).

The following table gives the intervals between study visits at defined visits to apply, as described in the protocol:

Table 1 Intervals between study visits for the investigational vaccine groups: AduFx, 2PedFx, PedFx, and Adu2Fx

Interval	Optimal length of interval ¹	Allowed interval ²
Visit 1 (Screening) → Visit 2 (1 st vaccination)	0 to 90 days	-
Visit 2 → Visit 3 (2 nd vaccination)	28 days	± 7 days
Visit 3 → Visit 5	7 days	± 1 day
Visit 3 → Visit 6	30 days	± 7 days
Visit 3 → Visit 7 (3 rd vaccination)	168 days	± 14 days
Visit 7 → Visit 9	7 days	± 1 day
Visit 7 → Visit 10	30 days	± 7 days
Visit 7 → Visit 11 (Challenge)	90 days	+ 14 days
Visit 11 → Visit 30	28 days	± 7 days
Visit 30 → Visit 31	62 days	± 14 days

¹ Whenever possible the investigator should arrange study visits within this interval.

² Subjects may not be eligible for inclusion in the according-to-protocol (ATP) cohort for analysis of immunogenicity and efficacy if they make the study visit outside this interval.

Table 2 Intervals between study visits for the investigational vaccine group: Adu1Fx

Interval	Optimal length of interval ¹	Allowed interval ²
Visit 1 (Screening) → Visit 2 (1 st vaccination)	0 to 90 days	-
Visit 2 → Visit 7 (2 nd vaccination)	196 days	± 14 days
Visit 7 → Visit 9	7 days	± 1 day
Visit 7 → Visit 10	30 days	± 7 days
Visit 7 → Visit 11 (Challenge)	90 days	+ 14 days
Visit 11 → Visit 30	28 days	± 7 days
Visit 30 → Visit 31	62 days	± 14 days

¹ Whenever possible the investigator should arrange study visits within this interval.

² Subjects may not be eligible for inclusion in the ATP cohort for analysis of immunogenicity and efficacy if they make the study visit outside this interval.

Table 3 Intervals between study visits for the infectivity control group

Interval	Optimal length of interval ¹	Allowed interval ²

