4.2.3. Safety

- Safety and reactogenicity of the investigational vaccine for each vaccination schedule:
 - Occurrence of solicited local and general AEs within seven days (day of vaccination and six subsequent days) after each vaccination.
 - Occurrence of unsolicited AEs within 30 days (day of vaccination and 29 subsequent days) after each vaccination, according to the Medical Dictionary for Regulatory Activities (MedDRA) classification.
 - Occurrence of AEs within 30 days (day of challenge and 29 subsequent days) after challenge, according to the MedDRA classification.
 - Occurrence of SAEs (all, fatal, related to investigational vaccine) within 30 days (day of vaccination and 29 subsequent days) after each vaccination, according to the MedDRA classification.
 - Occurrence of SAEs (all, fatal, related to investigational vaccine) during the whole study period (from Dose 1 [Day 0] up to study conclusion [Day 376]), according to the MedDRA classification.
 - Occurrence of AEs and SAEs leading to withdrawal from further vaccination from Dose 1 (Day 0) up to study conclusion (Day 376), according to the MedDRA classification, for each vaccinated subject.
 - Occurrence of pIMDs from Dose 1 (Day 0) up to study conclusion (Day 376), according to the MedDRA classification, for each vaccinated subject.
 - Occurrence of meningitis from Dose 1 (Day 0) up to study conclusion (Day 376), according to the MedDRA classification, for each vaccinated subject.
 - Occurrence of abnormal laboratory values at screening, Day 35, Day 58, Day 203, Day 226, the day of first parasitemia, and Day 314 for each vaccinated subject and at screening, the day of first parasitemia and Day 314 for the infectivity control subjects.

- Safety after sporozoite challenge in the infectivity control group.
 - Occurrence of AEs within 30 days (day of challenge and 29 subsequent days) after challenge, according to the MedDRA classification.
 - Occurrence of SAEs (all, fatal, related) from day of challenge (Day 286) to the end of the challenge phase (Day 314), according to the MedDRA classification.

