6.5. Analysis of safety

6.5.1. Analysis of safety planned in the protocol

The analysis of safety will be performed on the ITTS.

The percentage of subjects with at least one local AE (solicited and unsolicited), with at least one general AE (solicited and unsolicited) and with any AE during the 7-day or 30-day follow-up period after each vaccine dose and overall will be tabulated with exact 95% CI. The percentage of doses followed by at least one local AE (solicited and unsolicited), by at least one general AE (solicited and unsolicited) and by any AE during the 7-day or 30-day follow-up period will be tabulated with exact 95% CI. The same computations will be done for Grade 3 AEs, for any AEs considered related to vaccination and for any Grade 3 AEs considered related to vaccination.

The percentage of subjects reporting each individual solicited local AE (any grade and Grade 3) and each individual solicited general AE (any grade, Grade 3, any related, Grade 3 related, resulting in medically attended visit) during the 7-day follow-up period (Day 0-6) after each vaccine dose and overall will be tabulated for each group. Similarly, the percentage of doses followed by each individual solicited local and general AE will be tabulated, for the overall and for each vaccination course, with exact 95% CI.

For fever (fever is defined as temperature $\geq 37.5^{\circ}\text{C}/99.5^{\circ}\text{F}$ for oral, axillary or tympanic route, or $\geq 38.0^{\circ}\text{C}/100.4^{\circ}\text{F}$ for rectal route), the number and percentage of subjects reporting fever by half degree ($^{\circ}\text{C}$) cumulative increments during the first seven days (Day 0-6) after each vaccine dose and overall will be tabulated. Similar tabulations will be performed for any fever with a causal relationship to vaccination and Grade 3 ($> 39.0^{\circ}\text{C}$) causally related fever. The maximum temperature reported over the 7-day follow-up period (Day 0-6) overall doses will be tabulated.

The percentage of subjects reporting unsolicited AEs within 30 days (Day 0-29) after each vaccine dose (overall doses) and percentage of subjects reporting AEs after the sporozoite challenge will be tabulated by group and by MedDRA preferred term with exact 95% CI. Similar tabulation will be done for Grade 3 unsolicited AEs, for any causally related unsolicited AEs and for Grade 3 causally related unsolicited AEs.

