Template 31	Bar graph of the daily prevalence of swelling between day 1 and day 7 following each vaccination (Intent to treat set)	Post-text	CEMAX1BARG RAPH
Template 21	Percentage of subject with solicited general symptoms within 7 days following each vaccination and overall (Intent to treat set)	Post-text / Web disclosure	TCEMAX1FRE QSEV
Template 31	Bar graph of the daily prevalence of fatigue between day 1 and day 7 following each vaccination (Intent to treat set)	Post-text	CEMAX1BARG RAPH
Template 31	Bar graph of the daily prevalence of gastrointestinal between day 1 and day 7 following each vaccination (Intent to treat set)	Post-text	CEMAX1BARG RAPH
Template 31	Bar graph of the daily prevalence of headache between day 1 and day 7 following each vaccination (Intent to treat set)	Post-text	CEMAX1BARG RAPH
Template 22	Percentage of subjects with temperature by maximum value, within 7 days following each vaccination and overall (Intent to treat set)	Post-text	TCEMAX1TEMP
Template 31	Bar graph of the daily prevalence of temperature between day 1 and day 7 following each vaccination (Intent to treat set)	Post-text	CEMAX1BARG RAPH
Template 30	Summary of subjects taking a concomitant medication within 7-day following each vaccination and overall (Intent to treat set)	Post-text	specific
Template 30	Summary of subjects taking a concomitant medication during the challenge phase (Intent to treat set)	Post-text	specific
Template 23	Summary of subjects with at least one unsolicited adverse event classified by MedDRA Primary System Organ Class and Preferred Term within 30 days of any vaccination (Intention-to-treat set)	Post-text / Web disclosure	TAE1SOCPT
Template 25	Summary of subjects with unsolicited adverse events within 30 days of any vaccination by category (Intention-to-treat set)	Post-text	TAE1SOCPTS UMMARY
Template 23	Summary of subjects with at least one grade 3 unsolicited adverse evens classified by MedDRA Primary System Organ Class and Preferred Term within 30 days of any vaccination (Intention-to-treat set)	Post-text	TAE1SOCPT
Template 23	Summary of subjects with at least one related unsolicited adverse event classified by MedDRA Primary System Organ Class and Preferred Term within 30 days of any vaccination (Intention-to-treat set)	Post-text	TAE1SOCPT

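### The listed unsolicited-AE tables count subjects over any vaccination, although the three-dose arms are observed for 88 days and Adu1Fx for 60

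*SAP*

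**What the plan says.** The endpoint in Protocol 11.2.3, repeated in SAP 4.2.3, is "Occurrence of unsolicited AEs within 30 days (day of vaccination and 29 subsequent days) after each vaccination". For its analysis, SAP 6.5.1 plans the "percentage of subjects reporting unsolicited AEs within 30 days (Day 0-29) after each vaccine dose (overall doses", by group and preferred term, with the same for Grade 3, related and Grade 3 related events.

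The tables listed in SAP 12.4 for this purpose use Template 23, where subjects are "classified by MedDRA Primary System Organ Class and Preferred Term within 30 days of any vaccination", and Template 25, which summarises subjects by event category over the same period. The 30-day tables of serious, fatal serious and related serious events use Template 23 in the same way. None of these has a by-dose, per-vaccination or person-time version.

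Other parts of the SAP come closer to what is needed:

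- SAP 6.5.1 also plans the percentage of subjects after each dose, and the percentage of doses, followed by any AE over 7 or 30 days. It repeats this for Grade 3 and related AEs. Template 20 displays it, with solicited and unsolicited events combined.
- SAP 11.2.5 defines a per-dose denominator for unsolicited symptoms.
- The title of the Template 23 shell allows vaccinations rather than subjects to be counted, but no listed table uses that option.

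Protocol 11.11 describes the secondary comparisons between schedules as descriptive, "with the aim to characterize the difference in immunogenicity, efficacy and safety between groups".

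**The concern.** Collection of unsolicited AEs opens for 30 days at each dose, so an arm with one dose fewer is observed for less time. The percentage of subjects with at least one event rises with observed time even if no event is caused by vaccine. In the listed unsolicited-only tables, the contrast between Adu1Fx and the other schedules therefore combines two things: any real effect of giving one dose fewer, and fewer days on which background events could be recorded. Nothing in the SAP tells the reader that the arms differ in this respect.

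The two-dose schedule is one of the stated study aims (Protocol 1.2.1), so this is a contrast that readers will look for.

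**Working it through.** **Inputs**

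- Window: Day 0 to Day 29 after each dose. Counted inclusively this is 30 days, which reproduces the plan's own figure. The documents state no total per arm.
- Three-dose arms (AduFx, 2PedFx, PedFx, Adu2Fx): Dose 1 on Day 0, and later doses "at Dose 2 (Day 28), one day post-Dose 2 (Day 29), at Dose 3 (Day 196), and one day post-Dose 3 (Day 197" as in the Protocol synopsis sampling schedule. Protocol Table 3 agrees.
- Adu1Fx: Dose 1 on Day 0, then "at Dose 2 (Day 196) and one day post-Dose 2 (Day 197".
- Allowed interval for "Visit 2 → Visit 3 (2 nd vaccination": 28 ± 7 days (SAP Table 1).
- 26 subjects per vaccine arm (Protocol 11.4).

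**Days of ascertainment (union of the windows)**

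- Three-dose arms: Days 0–57 (58 days, because the first two windows overlap on Days 28–29) + Days 196–225 (30 days) = 88 days.
- Dose 2 on Day 21: Days 0–50 (51 days) + 30 = 81. Dose 2 on Day 30 or later, up to Day 35: 30 + 30 + 30 = 90.
- Adu1Fx: Days 0–29 + Days 196–225 = 60 days.
- Ratio 88/60 = 1.47. Person-days with 26 subjects: 26 × 88 = 2288 against 26 × 60 = 1560.

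**Size of the background gap**

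Assume a constant background rate, equal in all arms, with no vaccine effect. If P60 is the percentage with at least one event in 60 days, then P88 = 1 − (1 − P60)^(88/60).

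| P60 (Adu1Fx) | P88 (three-dose) | Gap, points | Subjects of 26 |
|---|---|---|---|
| 10% | 14.3% | 4.3 | 2.6 vs 3.7 |
| 30% | 40.7% | 10.7 | 7.8 vs 10.6 |
| 50% | 63.8% | 13.8 | 13.0 vs 16.6 |
| 60% | 73.9% | 13.9 | 15.6 vs 19.2 |
| 70% | 82.9% | 12.9 | 18.2 vs 21.6 |

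Over this range the gap is about 4 to 14 points, or 1 to 4 subjects of 26. At P60 = 50%, the limits of 81 and 90 days give 60.8% and 64.6% instead of 63.8%.

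The gap shrinks at both ends. At P60 = 90% it is 96.6 − 90 = 6.6 points. For a rare event with 2% per 30 days, P60 = 1 − 0.98² = 4.0% and P88 = 1 − 0.98^(88/30) = 5.8%, a gap of under 2 points. That is nearer to what a single preferred term or a Grade 3 row would show.

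**Effect of a per-dose denominator**

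SAP 11.2.2 assigns an event to the most recent dose. The windows are then 28, 30 and 30 days in the three-dose arms (88/3 = 29.3 per dose) and 30 and 30 days in Adu1Fx. With full compliance there are 26 × 3 = 78 and 26 × 2 = 52 doses. With daily rate λ = −ln(1 − P60)/60, the percentage of doses followed by an event is [(1 − e^(−28λ)) + 2(1 − e^(−30λ))]/3 against 1 − e^(−30λ):

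- P60 = 30%: 16.0% against 16.3%
- P60 = 50%: 28.7% against 29.3%
- P60 = 70%: 44.5% against 45.2%

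The background gap almost disappears.

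**The case against.** The strongest reply is that the percentage of subjects over the whole course is a proper measure of what a schedule costs its recipients. The safety objectives are stated for each schedule, and having one dose fewer, with one post-dose period fewer, is part of what Adu1Fx is. That stands. A reader might infer that Adu1Fx is made to look safer by construction. The documents do not support this: only background events in the 28 extra days are an artefact, fewer doses may truly cause fewer AEs, and a real effect could outweigh the artefact.

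A reader might also infer that the planned tables cannot separate the two components, or that only pooled per-subject figures are planned. That goes too far as well. Template 20 reports 30-day percentages after each vaccination, per subject and per vaccination, and a comparison within one 30-day window has essentially no duration problem. The listed related-AE tables should leave out many background events. Each helps only in part. Template 20 pools solicited with unsolicited AEs, so the unsolicited share cannot be read off, and causality is judged by the investigator in an open-label study.

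Nor is it right that nothing is collected in Adu1Fx between Days 30 and 195. Whole-study SAEs, pIMDs and meningitis are followed "from Dose 1 [Day 0] up to study conclusion [Day 376" in every vaccine arm, and the three-dose arms have a similar gap for other unsolicited AEs (Days 58–195).

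Finally, SAP 7 calls all analyses descriptive, and with 26 per arm the artefact lies inside the sampling uncertainty. An exact 95% interval at 13/26 runs from about 30% to 70%, and a gap of this size would reach two-sided 5% significance only about 7% to 19% of the time. This limits the harm, but the shift is systematic and readers will still compare the percentages side by side.

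**Conclusion.** The point holds for the unsolicited-only 30-day tables, including the 30-day SAE tables. Observation is 88 days (81 to 90 within the visit window) against 60, these tables report only subjects over any vaccination, and background events alone favour Adu1Fx. The shift is roughly 4 to 14 points, or 1 to 4 of 26 subjects, for assumed overall AE percentages of 10% to 70% over 60 days, and smaller for rare events. It rests on a constant background rate, equal across arms, which the documents do not supply.

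The point does not extend to SAEs, pIMDs or meningitis over the whole study, and it does not make the per-subject percentage invalid as a measure of schedule burden. It is a gap in the table list, made relevant by the Protocol's aim of describing safety differences between groups.

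**What to change.** - Keep the per-subject tables as a measure of schedule burden, and add a footnote giving 88 days of ascertainment in the three-dose arms and 60 in Adu1Fx.
- Add to SAP 12.4 the version of Template 23 that counts vaccinations followed by an event, for all, Grade 3 and related unsolicited AEs, with the per-dose denominator already defined in SAP 11.2.5.
- Show it by dose number as well as pooled, because the mix of full and fractional doses differs: fractional doses are 1 of 3 in AduFx, 2PedFx and PedFx, 2 of 3 in Adu2Fx and 1 of 2 in Adu1Fx. Print the study month beside the dose number, since SAP 11.2.2 numbers doses by order and Dose 2 in Adu1Fx is the Month 7 dose.
- Optionally add a rate per person-day of the collection window.
- Base any statement comparing unsolicited AEs between schedules on these tables.

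No new data are needed. The cost is a short change to the SAP and a few extra post-text tables.

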6.5.2. Additional considerations

A summary of subjects with all combined solicited (regardless of their duration) and unsolicited adverse events will be provided. Solicited adverse events will be coded by MedDRA as per the following codes:

Solicited symptom	Lower level term code	Corresponding Lower level term decode
FATIGUE	10016256	Fatigue
FEVER	10016558	Fever
GASTROINTESTINAL	10017944	Gastrointestinal disorder
HEADACHE	10019211	Headache
PAIN	10022086	Injection site pain
REDNESS	10022098	Redness at injection site
SWELLING	10053425	Swelling at injection site

The following analysis will be performed if at least 5 subjects have used concomitant vaccination during the 7-day follow-up period (Day 0-6) after study vaccination during the full study period.

The percentage of subjects using any concomitant vaccination during the 7-day follow-up period (Day 0-6) after study vaccination will be summarized by group after each dose and overall. The percentage of subjects using concomitant vaccination during the entire sporozoite challenge will be summarized by group.

Note that the study will be converted in CDISC. Accordingly protocol Day 0-Day N will be replaced by Day 1-Day N+1 for the statistical analysis.

